5.4 Rule of exclusion criteria of analysis sets

Table 1 *Protocol deviations that cause subjects to be excluded*

Deviation ID	Description of Deviation	Exclusion in Analyses
I1	Informed consent not obtained	Excluded from all analyses
I3	Subject aged < 18	Excluded from PP analysis
I4	Subject not diagnosed with RRMS	Excluded from all efficacy analyses
I5	Subject with EDDS > 6.0 at baseline visit	Exclude from PP analysis
I6	Subject not stable on Fingolimod for at least 28 days and at most 4 months prior to screening	Excluded from PP analysis
I7	Evidence of acute relapse within 30 days prior to baseline visit	Excluded from PP analysis
E1	Forbidden concomitant medication	Case by case review: excluded from PP analysis
E3	Subject is suffering from a cardiovascular condition	Case by case review: excluded from PP analysis (if relevant for primary parameter)
E4	Subject suffering from severe respiratory disease	Case by case review: excluded from PP analysis
E5	Subjects with history of specific MRI findings	Excluded from PP analysis
E7	Subject with a history of a malignancy of any organ system within the past 5 years	Excluded from PP analysis (Exception: localized basal cell carcinoma of the skin)
E8	Use of other investigational drug/therapy within 90 days or 5 half-lives of screening	Case by case review: excluded from PP analysis
E9	Pregnant or nursing women	Excluded from PP analysis
E10	Subject with any ophthalmologic reason for RNFL pathology other than MS	Case by case review: excluded from PP analysis
E11	History or active severe myopia	Case by case review: excluded from PP analysis
E12	Acute optic neuritis within the last 6 months prior to screening	Excluded from PP analysis

Deviation ID	Description of Deviation	Exclusion in Analyses
E13	Evidence of advanced diabetic retinopathy	Excluded from PP analysis
E14	Presence of retinal conditions	Case by case review: excluded from PP analysis
E15	Concomitant use of drugs that may directly affect retinal structure and function	Case by case review: excluded from PP analysis
S1	Treatment regime changed	Excluded from PP analysis
O1	Baseline OCT measurements not performed	Excluded from PP analysis
O3	Difference between visit 7 and baseline \leq 1035 days	Excluded from PP analysis

Table 2 Subject Classification

Analysis Set	PD ID that cause subjects to be excluded	Non-PD criteria that cause subjects to be excluded
ENR	NA	Not having informed consent; Not having screening epoch disposition page (i.e. date for Screening visit, vis1n=1)
SAF	NA	No dose of fingolimod taken
FAS	I1	Not in SAF No post-baseline efficacy data are collected
PPS	I1, I3, I4, I5, I6, I7 E1, E3 to E15 S1, O1, O3	

6 Reference

None

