5.1 Inclusion/exclusion criteria

Inclusion Criteria

Patients eligible for inclusion in this study have to fulfill all of the following criteria:

1. Written informed consent must be obtained before any assessment is performed.
2. Male or female subjects aged 18-65 years.
3. Subjects with relapsing remitting MS defined by 2010 revised McDonald criteria (see [Appendix 4](#)).
4. Patients with Expanded Disability Status Scale (EDSS) score of 0-6.0 inclusive (see [Appendix 6](#)).
5. Patients stable on immunomodulatory treatment with fingolimod for at least 28 days and at most 4 months prior to screening according to local label
6. Neurologically stable with no evidence of relapse within 30 days prior to inclusion date (visit 2)
7. Sufficient ability to read, write, communicate and understand

Exclusion Criteria

Patients fulfilling any of the following criteria are not eligible for inclusion in this study:

1. Patients who have been treated with:

- systemic corticosteroids or immunoglobulins within 1 month prior to screening;
 - immunosuppressive medications such as azathioprine, cyclophosphamide, or methotrexate within 3 months prior to screening;
 - monoclonal antibodies (including natalizumab) within 3 months prior to screening;
 - mitoxantrone within 6 months prior to screening
 - cladribine at any time.
2. Patients with any medically unstable condition, as assessed by the primary treating physician at each site.
 3. Patients with any of the following cardiovascular conditions :
 - history of myocardial infarction or with current unstable ischemic heart disease;
 - Heart failure (NYHA III-IV) or any severe cardiac disease as determined by the Investigator (see [Appendix 5](#));
 - history or presence of a second-degree AV block, Type II or a third-degree AV block
 - patients receiving Class Ia (ajmaline, disopyramide, procainamide, quinidine) or III antiarrhythmic drugs (e.g., amiodarone, bretylium, sotalol, ibutilide, azimilide, dofetilide);
 - proven history of sick sinus syndrome;
 - uncontrolled hypertension
 4. Patients with severe respiratory disease, pulmonary fibrosis, or chronic obstructive pulmonary disease (Class III-IV).
 5. Patients with history of specific MRI findings (tumor, subdural haematoma, post-contusional changes, territorial stroke, neurodegenerative disorders, aneurysm/arteriovenous malformation, evidence of past macroscopic haemorrhage, or other relevant MRI findings that would interfere with evaluation)

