10.1 Populations for analysis

The safety set (SS) will consist of all enrolled patients for whom safety information was collected. Of note, the statement that a patient had no adverse events also constitutes a safety assessment.

The Full Analysis Set (FAS) will consist of all enrolled patients for whom data was collected and who have at least one post-baseline efficacy assessment. This will be analogous to the ITT population.

The Per Protocol Population will consist of all patients from the FAS-population, for whom no major protocol violations are reported. All reported protocol violations will be classified as minor or major in a data review meeting prior to data base lock.

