2.2 Analysis sets

The analysis sets were defined in section 10 of the Clinical Study Protocol (CSP):

The Safety Set (SAF) consists of all patients treated with investigational drug (fingolimod) for whom safety information was collected. Of note, the statement that a patient has had no adverse events also constitutes a safety assessment.

The Full Analysis Set (FAS) consists of all patients treated with investigational drug (fingolimod) for whom data was collected and who have at least one post-baseline efficacy assessment. This is analogous to the ITT population.

The Per Protocol Population consists of all patients from the FAS population, for whom no major protocol violations are reported. All reported protocol violations will be classified as minor or major in a data review meeting prior to data base lock.

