2.3.1 Patient disposition

The disposition of all enrolled patients displays the number and reasons of screening failures.

The disposition of all patients in the treatment period (i.w. who received at least one dose of fingolimod) displays the number and reasons for premature discontinuation from the study.

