2.8.1 Adverse events (AEs)

Adverse events which started before BL/M0 were listed only. Analyses were performed on AEs which started at/after BL/M0.

The incidence of adverse events is displayed with n, percentage and 95% confidence interval for the SAF. Here, different types of AEs are presented:

- (1) Any AE
- (2) AE with suspected relationship to fingolimod
- (3) AE leading to study drug dosage adjustment/temporary interruption
- (4) AE leading to permanent study drug discontinuation
- (5) Serious adverse event
- (6) Non-Serious AE
- (7) Death

For AEs of type (1) to (6) a two-level frequency table for MedDRA system organ classes (SOC) and Preferred Terms (PT) within SOC are presented. Here, a patient with multiple occurrences is counted only once on the respective class.

The maximum severity of (several) AEs occurring in a patient ist displayed for PTs within SOC, SOC and overall.

For AEs of type (7), (5), and (3) separate listings are generated.

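### The SAP's dose test for the Safety Set and the treatment period is not tied to baseline, so screening failures already taking fingolimod can enter the adverse-event denominator

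*SAP*

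**What the plan says.** The documents describe the safety population in three ways.

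- Protocol 10.1: "The safety set (SS) will consist of all enrolled patients for whom safety information was collected". There is no dose condition.
- SAP 2.2: the set "consists of all patients treated with investigational drug (fingolimod) for whom safety information was collected". This has two conditions, drug and safety data. The same section adds that "the statement that a patient has had no adverse events also constitutes a safety assessment".
- SAP 5.4, Table 2, SAF row: the only criterion for removal is "No dose of fingolimod taken". The safety-data condition does not appear.

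SAP 2.3.1 plans two disposition displays. One covers all enrolled patients and shows screening failures. The other covers the treatment period, meaning patients "who received at least one dose of fingolimod", and shows premature discontinuations. Neither dose test carries a date or a visit.

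For the numerator, SAP 2.8.1 states: "Analyses were performed on AEs which started at/after BL/M0". Earlier events are only listed. Incidence is then given as n, percentage and 95% confidence interval on the SAF.

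On the drug itself, Protocol 6.2 says the decision to prescribe is made independently of the study. Inclusion criterion 5 (Protocol 5.1) requires patients to be "stable on immunomodulatory treatment with fingolimod for at least 28 days and at most 4 months prior to screening".

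**The concern.** A rule of at least one dose normally separates screening failures from treated patients because the study starts the drug. Here it does not. A patient who fails screening on, say, EDSS, myopia or recent optic neuritis may have been taking fingolimod for weeks and so passes the dose test as written.

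The numerator is anchored to baseline and the denominator is not. A patient who stops at screening can add one to the denominator and cannot contribute an analysed event. The bias has one direction: incidences come out too low. Safety, and the frequency of macular edema in particular, is a stated secondary objective (Protocol 3.2; SAP 1.2). In the disposition tables, the same patients could appear as premature discontinuations from treatment.

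SAP 2.2 and Table 2 also differ in their conditions, so two programmers could derive different denominators from the same plan.

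**Working it through.** The documents give no expected Safety Set size, event rate or number of screening failures, so there is no stated figure to reproduce. The check is a logical one followed by dilution arithmetic.

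**Step 1. Whom does the dose test remove?**

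| Consented patient | Took fingolimod before screening? | Removed by Table 2? |
|---|---|---|
| Fails criterion 5 because the drug was never taken | No | Yes |
| Fails another criterion while on fingolimod | Yes | No |
| Eligible and entered at Visit 2 | Yes | No |

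The test does not separate the second row from the third.

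**Step 2. Does being enrolled separate them?** Not reliably. The protocol glossary places enrollment at consent. The ENR row of Table 2 asks only for consent and a screening disposition page, and SAP 2.3.1 reports screening failures among enrolled patients. Protocol 6.1 and Appendix 7 use the word differently, for passing entry. The term is not used consistently enough to act as a filter.

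**Step 3. Does the safety-information condition separate them?** Only partly. For a patient who fails to be enrolled, Protocol 6.1 asks only for the reason and demography; a patient with nothing more is outside the SAF under SAP 2.2. But Appendix 2 lists a 10 ml routine laboratory sample at V1, Protocol 8.2 makes SAEs reportable from consent, Protocol 8.1 has adverse events sought at each visit, and SAP 2.2 accepts a record of no events. SAP 2.8.1 itself expects pre-baseline events and lists them. Some screening failures can therefore satisfy the condition.

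**Step 4. Is anything else anchored?** Yes. Exposure in SAP 2.4.1 is the last administration date minus the Visit 2 date plus 1 day, which is undefined for a patient with no Visit 2. The event cut-off in SAP 2.8.1 is baseline. Only the Safety Set is unanchored.

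**Step 5. Size.** Let n = patients who reach baseline, k = screening failures retained with no countable event, and x = patients with an event.

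Reported incidence = x/(n + k); dilution factor = n/(n + k).

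Inputs: n = 100, taken from the planned sample of about 100 (SAP 3). The values of k and x are assumptions. Intervals are Clopper-Pearson, also an assumption, since the SAP names no method.

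| k | Factor | x = 2 | x = 80 |
|---|---|---|---|
| 0 | 100/100 = 1.000 | 2.0% (0.2-7.0) | 80.0% (70.8-87.3) |
| 5 | 100/105 = 0.952 | 1.9% (0.2-6.7) | 76.2% (66.9-84.0) |
| 10 | 100/110 = 0.909 | 1.8% (0.2-6.4) | 72.7% (63.4-80.8) |
| 20 | 100/120 = 0.833 | 1.7% (0.2-5.9) | 66.7% (57.5-75.0) |

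If the 100 were counted at consent instead, with k of them failing, the factor is (100 - k)/100: 0.95, 0.90 and 0.80 for k = 5, 10 and 20.

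**Step 6. Reach.** Table 2 also removes from the FAS anyone without post-baseline efficacy data. A screening failure has none, so the primary RNFLT analysis is untouched, and so is the per-protocol set drawn from the FAS.

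**The case against.** The best defence is that the intent can be read from the surrounding text. SAP 2.4.1 starts exposure at Visit 2 and calls earlier use pre-treatment; SAP 2.3.1 shows screening failures in a display of their own; and SAP 2.2 speaks of patients treated with investigational drug. Read together, these suggest that a dose means a dose on study. If SAP 2.2 governs and no screening failure has safety data, k = 0 and nothing is diluted. The study is single-arm and descriptive, and even the 20-failure case moves a 2% rate only to 1.7%. SAP 2.1 and Protocol Table 7-1 are not in the text available for this review, and an anchor might be stated there.

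Much of this stands. The intent is probably as described, and the effect on rare events is small against the width of the interval. But intent is not the rule. Table 2 is what a programmer would implement, and as written it retains on-drug screening failures. For common events the shift is visible: 80% becomes 67% at k = 20.

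Three stronger readings are tempting, and the documents do not support them.

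- *The criterion excludes nobody.* Pre-treatment is an inclusion criterion checked after consent, so a consented patient who never took fingolimod is excluded.
- *Every screening failure enters the denominator.* SAP 2.2 requires safety information, and Protocol 6.1 does not require it for these patients. Entry is possible, not certain.
- *Macular edema suspected at baseline would be counted as event-free.* Appendix 7 has this found at baseline. An event dated then falls at or after BL/M0 and could be counted.

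**Conclusion.** The point holds as a defect in a stated rule. The dose test in Table 2 and SAP 2.3.1 has no time anchor, it conflicts with SAP 2.2 on safety data, and in this design it does not remove screening failures who have taken fingolimod. Their number is unknown. Under the assumption of 100 baseline patients and 0 to 20 failures retained, incidences are multiplied by 1.00 to 0.83. Zero dilution is a genuine possibility, so a reader should not infer that the safety percentages are necessarily diluted.

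The consequences are confined to descriptive safety and disposition results and other summaries on the SAF. The point is worth correcting because the direction is always towards lower incidence, macular edema frequency is a named objective, and the correction needs no new data. If SAP 2.1 already ties study treatment to Visit 2, what remains is to align Table 2 with SAP 2.2.

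**What to change.** Reconcile SAP 2.2, SAP 2.3.1 and the SAF row of Table 2 under one definition. The Safety Set and the treatment period should both consist of patients confirmed eligible and entered at Baseline (Visit 2), with at least one fingolimod dose on or after that date and safety information collected. This matches the exposure start in SAP 2.4.1 and the event cut-off in SAP 2.8.1.

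The words on confirmed eligibility and entry are needed. Attendance at Visit 2 plus a dose would not be enough, because a patient turned away for macular edema suspected at that visit could meet both conditions.

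List separately any on-drug events found in patients who were not entered, including macular edema suspected at baseline, so that they are neither lost nor mixed into the incidence.

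Cost: a few lines of text. Incidences may become slightly less favourable.
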